### 7.3.5 OVERALL SURVIVAL

OS is defined as the time after having completed at least 85% of the prescribed SBRT dose up to time of death, or 2 years from last SBRT dose, whichever occurs first.

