##### 3.2.2 SECONDARY ENDPOINTS

Endpoint	Start	End
1. Localized control rate: Incidence of progressive disease within or at the planned tumor volume (PTV) margin		Time of progression, transplantation, death or 2-years after last SBRT dose, whichever occurs first.
2. Incidence of intrahepatic progressive disease		
3. Incidence of extrahepatic progressive disease		
4. Proportion of participants that proceed to transplantation	First dose of SBRT	
5. Overall Survival		Time of death or 2-years after last SBRT dose
6. Incidence of non-classic RILD, defined as grade 4 aspartate aminotransferase or alanine aminotransferase elevation, or an increase in CP score of $\geq 2$ within 1 week to 3 months after completing SBRT (Appendix A)		3 months after last SBRT dose

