### 7.3.3 LOCAL CONTROL RATE

Local control is defined as the absence of progressive disease (per Section 7.3.1) within the PTV or at the PTV margin, measured from time of first SBRT dose to time of progression or transplantation, or 2 years from last SBRT dose, whichever occurs first.

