### 7.3.4 INTRAHEPATIC PROGRESSION-FREE SURVIVAL

Intrahepatic progression-free survival (PFS) is defined as the development of intrahepatic recurrent or new disease within any section of the liver, including the PTV. The consideration of whether a lesion is within or adjacent to the PTV is determined by the individual site investigator. Intrahepatic PFS is measured from time of first SBRT dose to time of progression or transplantation, or 2 years from last SBRT dose, whichever occurs first.

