#### 9.2.2 ANALYSIS OF PRIMARY ENDPOINT

Using the efficacy analysis set, the proportion of transplant eligible participants at 1 year (per Milan criteria, Section 7.5) will be measured from time of first SBRT dose, reported with 95% exact confidence interval (CI).

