#### 9.2.3 ANALYSIS OF THE SECONDARY ENDPOINTS

Using the efficacy analysis set, the estimate of local control rate, intrahepatic progression free survival, and overall survival, will be plotted using Kaplan-Meier curve and reported with median survival and 95% CI if available. Using the same efficacy analysis set, the proportion of participants that proceed to transplantation, will be measured and reported with 95% CI.

Non-classic RILD, liver toxicity defined as a  $\geq 2$  increase in CP score (**Appendix A**), and liver toxicity per CTCAE v5.0, will be estimated along with an exact CI using the safety analysis set.

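### Overall survival has two inconsistent time origins (85% of the dose completed in 7.3.5, first SBRT dose in 3.2.2), and the origin must be settled together with the analysis set

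*Combined protocol and SAP*

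**What the plan says.** Section 7.3.5 gives the definition: "OS is defined as the time after having completed at least 85% of the prescribed SBRT dose up to time of death", with a cap at 2 years from the last SBRT dose. The secondary-endpoint table in 3.2.2 lists OS with the matching end, "Time of death or 2-years after last SBRT dose". The Start column of that table has one entry, "First dose of SBRT". In the extracted text it stands on the row for the proportion proceeding to transplantation, and the other Start cells, including the one for OS, are empty.

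The neighbouring endpoints use the first dose. Local control in 7.3.3 is "measured from time of first SBRT dose to time of progression or transplantation, or 2 years from last SBRT dose, whichever occurs first". Section 7.3.4 says "Intrahepatic PFS is measured from time of first SBRT dose to time of progression or transplantation". The primary endpoint starts at the start of SBRT in 3.2.1 and at the first dose in 9.2.2.

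On analysis, 9.2.3 says that, in the efficacy analysis set, "intrahepatic progression free survival, and overall survival, will be plotted using Kaplan-Meier curve and reported with median survival and 95% CI if available". It does not say where the OS clock starts. Section 9.1 limits the efficacy set to participants who received at least 85% of the prescribed dose, and defines a safety set that counts participants from their first fraction.

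**The concern.** The two sections agree on when OS ends and disagree on when it begins. Two analysts who each follow the protocol could draw different OS curves and report different medians from the same data. If the origin is not fixed in advance, it can be chosen after the survival times are known.

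The 7.3.5 origin also puts OS on a different clock from the other time-to-event endpoints. A participant who is event-free to the end of follow-up has OS censored at exactly 2 years, because the 85% milestone falls on the last dose. The same participant's local control and intrahepatic PFS times are censored at 2 years plus the treatment course, so the PFS time exceeds the OS time. Section 1.3 says the pilot is meant to help estimate bridging efficacy against historical controls, so a reader needs to know which interval was measured.

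**Working it through.** **1. The plan's own figures.** Section 9.1 gives the 85% thresholds as 34, 30 and 25.5 Gy. Check: 0.85 × 40 = 34; 0.85 × 35 = 29.75 (printed as 30); 0.85 × 30 = 25.5. These reproduce, apart from rounding. The sample size of 15 in 9.3.1 rests on a 20% chance that a plan fails the dosimetric constraints: 1 − 0.80^15 = 0.965, which exceeds 0.95. It reproduces, and OS plays no part in it.

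**2. When 85% is reached.** Section 5.1.3 gives the total dose and five fractions. I assume equal fractions. After four fractions the share delivered is 32/40 = 28/35 = 24/30 = 80%, below 85% at every dose level. The milestone in 7.3.5 is therefore the fifth fraction.

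**3. Length of the course, g (first to fifth fraction).**
- Weekday rule in 5.2, every other day, weekend days moved to Monday: 9, 10, 9, 11 and 10 days for Monday to Friday starts.
- Day 1 to Day 9 grid in 6.8: 8 days. No weekday start allows five alternate days without meeting a weekend, so 9–11 is the better on-schedule figure.
- Every interval delayed by the 7 days allowed in 6.8: 4 × (2 + 7) = 36 days.
- Every gap at the 14-day limit in 5.2: 4 × 14 = 56 days, or 4 × (2 + 14) = 64 days if the 14 days are added to the planned interval.

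Sections 6.8 and 5.2 give different delay limits that need reconciling; I carry both without preferring either.

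**4. Scale.** Section 1.2.1 cites a median OS of 17.0 months for CP-B in a phase 1-2 trial. 17.0 × 30.4375 = 517 days.

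| g (days) | g / 517 |
|---|---|
| 9 | 1.7% |
| 11 | 2.1% |
| 36 | 7.0% |
| 56 | 10.8% |
| 64 | 12.4% |

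**5. Against sampling error.** Assume exponential survival, a 17.0-month median and all 15 deaths observed. An approximate 95% interval for the median is 17.0 × exp(±1.96/√15) = 10.2 to 28.2 months. Censoring at 2 years would widen it. The on-schedule shift is 9/30.4375 to 11/30.4375, or 0.30 to 0.36 months.

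**6. Effect of moving the origin alone.** For each participant, OS from first dose = OS from 85% + g. Nobody in the efficacy set can have died during g, since reaching 85% is the condition for entry. In that set a first-dose curve stays at 100% until at least the shortest g, and its median is longer by about g. All of the added time is guaranteed survival.

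**The case against.** The strongest objection is that the 7.3.5 origin is coherent with the analysis set. Participants enter the efficacy set when they reach 85% of the dose, and 7.3.5 starts the clock at that moment, which is a landmark definition. Moving time zero to the first dose while keeping the 85% requirement would add survival time that every analysed participant must have. This stands. It means the origin cannot be corrected without also changing the set, and that local control and intrahepatic PFS already carry this guaranteed time.

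Second, the conflict with 3.2.2 depends on reading the Start entry as a merged cell. That is an inference, though a natural one: no other row has a Start entry, and the 3.2.3 table shows the same pattern, with its Screening entry on the second of the two quality-of-life rows. If the cell did not cover OS, 3.2.2 would give OS no start, and the mismatch with 7.3.3 and 7.3.4 would remain.

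Third, 7.3.5 may be a loosely worded evaluability condition, echoing 7.1 and 9.1, rather than a time origin. That is possible, but as written it defines the interval and would still need changing.

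Fourth, the shift is small beside the sampling error for 15 participants, and OS is descriptive with no hypothesis test. This stands too, and limits the weight of the point.

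**Conclusion.** The inconsistency holds. OS times in the efficacy set depend on which section is followed, and the difference is the length of the treatment course: about 9–11 days on schedule, 36 days with a 7-day delay at every interval, and 56 days or more only if every gap reaches 14 days. The last two are permitted limits, not expectations. The result rests on equal fractions and on the merged-cell reading of 3.2.2; the percentages use the cited CP-B median for scale only.

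Three stronger conclusions are tempting, and the documents do not support them:
- A reader might infer that OS could not be compared with figures counted from the start of SBRT. An offset of about 2% does not prevent comparison, and the protocol does not give the time origin of the 17.0-month figure.
- A reader might infer that leaving the treatment period off the clock biases OS. In a set conditioned on reaching 85%, leaving it off is the consistent handling; the fault is the unlabelled conflict with 3.2.2 and the other endpoints.
- A reader might infer that the trial's main result is affected. The primary endpoint has its own stated origin, and neither it nor the sample size depends on OS.

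This is a modest point, worth correcting because it is cheap and because the origin should be fixed before analysis.

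**What to change.** In 7.3.5 and 9.2.3, define OS as the time from the first SBRT dose to death, censored at 2 years after the last dose as now, and estimate it in all participants who received at least one fraction, which is the existing safety analysis set. The first-dose origin then carries no guaranteed survival time. If OS in the 85%-dose efficacy set is also wanted, report it from the date 85% was reached, labelled as a landmark analysis. Show the first-dose start explicitly on the OS row of 3.2.2, and take OS out of the list of efficacy-set endpoints in 7.1 and 9.1, or mark it there as the landmark version.

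The cost is a few sentences, and fraction dates should already be in the treatment record. There are two consequences to accept. The main OS estimate may be slightly less favourable, because participants who received less than 85% of the dose are counted. And because 5.2 removes participants with long interruptions from the study, the plan should say whether their vital status is still recorded or whether they are censored at removal.

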## 7.4 RESPONSE REVIEW

Response assessment will be determined by the investigator.

## 7.5 MILAN CRITERIA

Participant eligibility for transplantation will be based on guidelines reported by Mazzaferro et al. To be considered eligible for liver transplantation, participants with HCC must have disease as follows:

- Single tumor with diameter  $\leq 5$  cm **OR** up to 3 tumors, each with diameter  $\leq 3$  cm, **AND**
- No major vessel or extra-hepatic involvement.

## **8. SAFETY**

### **8.1 SPECIFICATION OF SAFETY PARAMETERS**

The Investigator is responsible for monitoring the safety of participants who have enrolled in the study. Safety assessments will be based on medical review of adverse events and the results of safety evaluations at specified time points as described in Section 6.8, Schedule of Events. Any clinically significant adverse events persisting at the end of treatment visit will be followed by the Investigator until resolution/stabilization or death, whichever comes first.

### **8.2 DEFINITIONS**

#### **8.2.1 ADVERSE EVENT (AE)**

An adverse event is defined as any undesirable physical, psychological or behavioral effect experienced by a participant during their participation in an investigational study, in conjunction with the use of the investigational product, whether or not considered intervention-related (21 CFR 312.32 (a)). In general, this includes signs or symptoms experienced by the participant from the time of signing the informed consent to completion of the study.

AEs may include, but are not limited to:

- Subjective or objective symptoms spontaneously offered by the participant and/or observed by the Investigator or medical staff.
- Clinically significant laboratory abnormalities.
- A significant worsening of the participant's condition from study entry.
- Disease signs and symptoms and/or laboratory abnormalities existing prior to the use of the study treatment that resolve but then recur after treatment.
- Disease signs and symptoms and/or laboratory abnormalities existing prior to the use of the study treatment which increase in frequency, intensity, or a change in quality after treatment.

#### **8.2.2 SERIOUS ADVERSE EVENT (SAE)**

An AE or suspected adverse reaction is considered "serious" if, in the view of either the Investigator, it results in any of the following outcomes:

- Death,
- A life-threatening adverse event,
- In-patient hospitalization or prolongation of existing hospitalization,
- A persistent or significant incapacity or substantial disruption of the ability to conduct normal life functions, or
- A congenital anomaly/birth defect.

Important medical events that may not result in death, be life-threatening, or require hospitalization may be considered serious when, based upon appropriate medical judgment, they may jeopardize the participant and/or participant may require medical or surgical intervention to prevent one of the outcomes listed in this definition. Examples of such medical events include:

- Allergic bronchospasm requiring intensive treatment in an emergency room or at home,
- Blood dyscrasias or convulsions that do not result in in-patient hospitalization, or

- The development of drug dependency or drug abuse.

#### 8.2.3 UNANTICIPATED PROBLEMS (UP)

The Office for Human Research Protections (OHRP) considers UPs involving risks to participants or others to include, in general, any incident, experience, or outcome that meets all of the following criteria:

1. Unexpected in terms of nature, severity, or frequency given (a) the research procedures that are described in the protocol-related documents, such as the IRB-approved research protocol and informed consent document; and (b) the characteristics of the participant population being studied;
2. Related or possibly related to participation in the research (“possibly related” means there is a reasonable possibility that the incident, experience, or outcome may have been caused by the procedures involved in the research); and
3. Suggests that the research places participants or others at a greater risk of harm (including physical, psychological, economic, or social harm) than previously known or recognized.

This study will use the OHRP definition of UP.

#### 8.2.4 SEVERITY OF EVENT

The Investigator will grade the severity of each AE using, when applicable, the current version of the [CTCAE v5.0](#). In the event of an AE for which no grading scale exists, the Investigator will classify the AE as defined below:

- **Mild** (grade 1) – An event that is usually transient in nature and generally not interfering with normal activities
- **Moderate** (grade 2) – An event that is sufficiently discomforting to interfere with normal activities
- **Severe** (grade 3) – An event that is incapacitating with inability to work or do usual activity, or inability to work or perform normal daily activity
- **Life-threatening/debilitating** (grade 4) – An event that puts the participant at immediate or potential risk of death, requires hospitalization, or which drastically impacts a participant’s well-being
- **Fatal** (grade 5)

#### 8.2.5 ASSESSMENT OF CAUSALITY RELATIONSHIP TO STUDY AGENT

For all collected AEs, the clinician who examines and evaluates the participant will determine the AE’s causality based on temporal relationship and his/her clinical judgment. The degree of certainty about causality will be graded using the categories below.

- *Definite* – The AE is clearly related to the study treatment.
- *Probable* – The AE is likely related to the study treatment.
- *Possible* – The AE may be related to the study treatment.
- *Unlikely* – The AE is doubtfully related to the study treatment.
- *Unrelated* – The AE is clearly NOT related to the study treatment.

### 8.3 EXPECTEDNESS

The investigator will be responsible for determining whether an AE is expected or unexpected. An AE will be considered unexpected if the nature, severity, or frequency of the event is not consistent with the risk information previously described for the study agent.

## **8.4 ADVERSE EVENT LIST(S)**

### **8.4.1 ADVERSE EVENT LIST FOR SBRT**

Rates of non-classical RILD (defined as a CP elevation of 2 or more within 3 months after radiation) are reported to be in the range of 20-30%.

Rates of Grade CTCAE 1-2 toxicities are reported to range from 0-27% and Grade 3-4 toxicities are observed in around 5%. The most commonly reported toxicities are fatigue, right upper quadrant pain, low-grade pyrexia, and elevation in transaminase. Minor pain, fever and chills (Grade 1) is observed in 14% of patients. Gastric ulceration and esophagitis occurred at rates of 7% (Grade 2) and 3% (Grade 3), respectively.

## **8.5 ADVERSE EVENT ASSESSMENT AND FOLLOW-UP**

The occurrence of an UP, AE or SAE may come to the attention of study personnel during study visits and interviews of a study participant presenting for medical care, or upon review by a study monitor. All AEs including local and systemic reactions not meeting the criteria for SAEs will be captured on the appropriate CRF. Information to be collected includes event description, time of onset, clinician's assessment of severity, seriousness, expectedness, relationship to study product (assessed only by those with the training and authority to make a diagnosis), and date of resolution/stabilization of the event. All AEs occurring while on study must be documented appropriately regardless of relationship. All AEs will be followed to adequate resolution.

Any medical condition that is present at the time that the participant is screened will be considered as baseline and not reported as an AE. However, if the study participant's condition deteriorates at any time during the study, it will be recorded as an AE.

Changes in the severity of an AE will be documented to allow an assessment of the duration of the event at each level of severity to be performed. AEs characterized as intermittent require documentation of onset and duration of each episode.

At each study visit, the Investigator will inquire about the occurrence of AE/SAEs since the last visit. Events will be followed for outcome information until resolution or stabilization.

AEs will be evaluated using the current version of the CTCAE v5.0 from the time the participant signs the consent form to 3 months following SBRT.

## **8.6 REPORTING PROCEDURES**

### **8.6.1 OHSU IRB REPORTING OF UNANTICIPATED PROBLEMS AND ADVERSE EVENTS**

Unanticipated Problems and AEs will be reported to OHSU IRB according to the policies, procedures and guidelines posted on the [OHSU IRB web site](#).

Events that must be reported by the Investigator to the IRB are detailed in the OHSU IRB **Investigator Guidance: Prompt Reporting Requirements (HRP-801)**. At a minimum, events requiring reporting to the IRB include:

- Any new or increased risk related to the research, including AEs or IND safety reports that require a change to the protocol or consent,
- New FDA black box warning,
- Publications identifying new risks,
- Data Safety Monitoring Board/Committee letters recommending changes or discussing new risks
- Unanticipated adverse device effect
- Unauthorized disclosure of confidential participant information

#### 8.6.2 MEDWATCH REPORTING

The Investigator is required to report AEs to the FDA through the MedWatch reporting program, even if the trial involves a commercially available agent. Adverse events to be reported include any UPs (i.e., not listed in the package insert) and any SAEs with a suspected association to the investigational product.

Adverse events that occur during clinical studies are to be reported to FDA as specified in the investigational new drug/biologic regulations using Form FDA 3500, the MedWatch Voluntary Reporting form (available [here](#)), or completed [online](#). A copy of Form FDA 3500 and supporting materials will be kept on file in the study regulatory binder.

#### 8.6.3 REPORTING OF PREGNANCY

To ensure participant safety, each pregnancy in a participant on study treatment must be reported within 24 hours of learning of its occurrence. The pregnancy should be followed to determine outcome, including spontaneous or voluntary termination, details of the birth, and the presence or absence of any birth defects, congenital abnormalities, or any pregnancy- or childbirth-related and/or newborn complications.

The pregnancy should be recorded on the CRF and reported by the Investigator to the IRB. Pregnancy follow-up should be reported using the same form. Any SAE experienced during pregnancy must be reported.

If while on study treatment a participant's sexual partner becomes pregnant, the pregnancy and pregnancy outcomes must also be reported as described above. Consent to report information regarding the pregnancy should be obtained from the pregnant individual.

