Secondary Endpoints	
 
1. Incidence of progressive disease within or at the planned tumor volume (PTV) margin (i.e. local control)
 
2. Incidence of progressive disease within any section of the liver, including the PTV (e.g. intrahepatic disease free survival)
 
3. Incidence of progressive disease outside of the liver (e.g. extrahepatic disease free survival)
 
4. Overall Survival
 
5. Proportion of participants that proceed to transplantation
 
6. Incidence of non-classical radiation-induced liver disease (RILD), defined as grade 4 aspartate aminotransferase or alanine aminotransferase elevation, or an increase in CP score of <math>\geq 2</math> within 1 week to 3 months after completing SBRT.
 

	7. Incidence of liver toxicity per CTCAE v5.0 within 1 week to 3 months after completing SBRT.
Exploratory Endpoints	
 
1. QoL scores for EORTC QLQ-C30 questionnaire
 
2. QoL scores for Functional Assessment of Cancer Therapy-Hepatobiliary (FACT-Hep) questionnaire
 
3. At time of transplantation, histopathologic changes in irradiated tumor sites relative to uninvolved liver tissue will be assessed
 

Number of Participants	15
Duration of Therapy	SBRT will be administered as 5 fractions every other day (~10 day)
Duration of Follow Up	Time of progression, or transplantation, or 2-years after last SBRT dose, whichever occurs first
Key Inclusion Criteria	
 
1. Participants aged <math>\geq 18</math> years
 
2. Patient diagnosed with HCC and recommended for LTX
 
3. Meets clinical criteria for eligibility for SBRT to the target lesion
 
4. Childs-Pugh Class B8 or higher
 
5. Eastern Clinical Oncology Group performance status <math>\leq 2</math>
 
6. Safe radiation treatment planning parameters that adhere to all organs at risk constraints per section 5.1 of the protocol. If normal organs at risk constraints (including at least 700cc of uninvolved liver) are unable to be met at the lowest dose modification (30 Gy in 5 fractions), the patient is deemed ineligible for SBRT and deemed a screen failure.
 

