### 4.2 PARTICIPANT EXCLUSION CRITERIA

An individual who meets any of the following criteria will be excluded from participation in this study:

1. Participants have any one of the following liver tumor characteristics:
  - a. have  $> 5$  liver tumors, or
  - b. maximal diameter  $> 5$  cm
2. Complete obstruction of portal venous flow to the segment of liver that includes the target lesion
3. Prior radiotherapy to the upper abdomen or radioembolization of the liver, or prior thermal

ablation to the target lesion.

4. For fiducial marker placement:
  - a. Have a gold allergy,
  - b. Any coagulopathy preventing safe fiducial placement
5. Contraindication to both contrast enhanced MRI and contrast enhanced CT (i.e. unable to undergo follow-up imaging or SBRT treatment planning)
6. Participation in another concurrent treatment protocol
7. Participant is pregnant or breastfeeding, or expecting to conceive or father children within the projected duration of the trial, starting with the screening visit through 120 days after the last dose of trial treatment.
8. Uncontrolled intercurrent illness, including but not limited to, ongoing or active infection, symptomatic congestive heart failure, uncontrolled hypertension, unstable angina pectoris, cardiac arrhythmia, interstitial lung disease, serious chronic gastrointestinal conditions associated with diarrhea, or psychiatric illness/social situations that would limit compliance with study requirement, substantially increase risk of incurring AEs or compromise the ability of the patient to give written informed consent

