#### 5.2 DOSING DELAYS AND MODIFICATIONS

SBRT will be delivered in a total of 5 fractions over two weeks, with treatments delivered every other day between Monday and Friday. SBRT will not occur on Saturdays, Sundays or holidays. There should be no more than a 14 day interruption between the planned administration of each fraction. Dosing interruptions lasting longer than 14 days between each fraction, for any reason, are considered an unacceptable and participants will be removed from

study and replaced with another participant. Participants removed from study will be treated per institutional standards or offered participation in another clinical trial if one is available. All dosing interruptions should be recorded in CRF.

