#### 5.3.1 CONTRACEPTION

SBRT may have adverse effects on a fetus in utero, and may have adverse effects on the composition of sperm. People may be enrolled if they are willing to use methods of birth control or are considered highly unlikely to conceive. Highly unlikely to conceive people are defined as: 1) surgically sterilized or biologically absent reproductive organs, or 2) postmenopausal (a woman who is  $\geq$  45 years of age and has not had menses for more than 1 year), or 3) not heterosexually active for the duration of the study. Birth control methods can either be two barrier methods or a barrier method plus a hormonal method to prevent pregnancy. Participants should start using birth control from study visit 1 throughout the study period up to 120 days after the last dose of study therapy.

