### 5.3.2 USE IN PREGNANCY

If a participant inadvertently becomes pregnant while receiving SBRT, the participant will immediately be removed from the study. The site will contact the participant at least monthly and document the participant's status until the pregnancy has been completed or terminated. The site will report the outcome of the pregnancy to Sponsor without delay and within 24 hours if the outcome is a serious adverse experience (e.g., death, abortion, congenital anomaly, or other disabling or life-threatening complication to the mother or newborn). The pregnancy will be recorded on the CRF and reported by the Investigator to the IRB. Refer to Section 8.6.

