#### 6.1.6 ADVERSE EVENT EVALUATION

Toxicities and adverse experiences will be assessed at each visit using the [CTCAE v5.0](#) and quantifying current Child-Pugh score to assess risk of RILD. Adverse events will be monitored from the time the participant signs the Consent Form up until 3 months following SBRT. Participants will be instructed to report all AEs during the study and will be assessed for the occurrence of AEs up until 3 months following radiation therapy. All AEs (serious and non-serious) must be recorded on the source documents and CRFs regardless of the assumption of a causal relationship with the study therapy.

For details on AE collection and reporting, refer to Section 8.6.

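### Mandatory pregnancy reporting is tied to study treatment (about 10 days as planned), although the protocol's own reproductive-risk period runs to 120 days after the last dose

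*Combined protocol and SAP*

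**What the plan says.** **Reporting and follow-up.** Section 8.6.3 says "each pregnancy in a participant on study treatment must be reported within 24 hours of learning of its occurrence", with follow-up of the pregnancy to its outcome. For partners the condition is "If while on study treatment a participant's sexual partner becomes pregnant". Section 5.3.2 opens with "If a participant inadvertently becomes pregnant while receiving SBRT" and attaches at least monthly contact until the pregnancy ends.

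**Risk period.** Section 5.3.1 names possible effects on a fetus and on sperm, and asks for birth control from study visit 1 "throughout the study period up to 120 days after the last dose of study therapy". Exclusion criterion 7 in Section 4.2 bars anyone expecting to conceive or father a child from screening "through 120 days after the last dose of trial treatment". The Summary of Changes (item 3) records that the contraception period in 5.3.1 was revised because it did not match the exclusion criteria.

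**Length of treatment.** The Synopsis says "SBRT will be administered as 5 fractions every other day (~10 day". Section 5.2 gives two weeks, "with treatments delivered every other day between Monday and Friday". The Schedule of Events (6.8) shows days 1 to 9.

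**Adverse events.** Section 6.1.6 monitors AEs from consent "up until 3 months following SBRT". The Schedule of Events and Section 8.5 use the same 3-month limit. Section 8.2.1 words it differently and lets AEs run in general to completion of the study.

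**The concern.** The protocol sets one period in which it regards conception as hazardous and another, far shorter, in which it expressly requires a pregnancy to be reported and followed. A pregnancy arising between the last fraction and day 120 lies inside the first period and outside the second. For a partner's pregnancy, the clause in 8.6.3 is the only explicit route in the documents, and Table 1 projects 11 of 15 participants to be male.

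What is at stake is safety information. Section 8.6.3 exists to collect pregnancy outcomes, birth defects and complications. Followed as written, it does not require that information for most of the time over which the protocol itself asks participants to avoid conception.

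**Working it through.** **Inputs**
- Treatment span *T*, in days from first to last fraction inclusive: Synopsis, Section 5.2 and the Schedule of Events.
- Post-treatment risk period: 120 days (Sections 4.2 and 5.3.1).
- AE capture after SBRT: 3 months, taken as 91 days (an assumption).

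**The plan's own treatment length.** Five fractions every other day, weekdays only, from a Monday start fall on days 1, 3, 5, 8 and 10, a span of 10 days. Other start days give 10 to 12 days. This reproduces the Synopsis figure of about 10. The Schedule of Events implies 9, and the two weeks in Section 5.2 imply at most 14.

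**Share of the window covered by the trigger.** The window is counted from first dose to 120 days after the last dose, so coverage = *T* / (*T* + 120).

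| Treatment span | *T* | Covered | Not covered |
|---|---|---|---|
| Schedule of Events, days 1 to 9 | 9 | 9/129 = 7.0% | 93.0% |
| Synopsis | 10 | 10/130 = 7.7% | 92.3% |
| Weekday calendar, longest | 12 | 12/132 = 9.1% | 90.9% |
| Section 5.2, two weeks | 14 | 14/134 = 10.4% | 89.6% |
| 7-day delay at every gap (Schedule of Events, footnote A) | 1 + 4 × (2 + 7) = 37 | 37/157 = 23.6% | 76.4% |
| 14 days between all fractions (Section 5.2) | 1 + 4 × 14 = 57 | 57/177 = 32.2% | 67.8% |
| 14 days added to every 2-day gap (Section 5.2) | 1 + 4 × (2 + 14) = 65 | 65/185 = 35.1% | 64.9% |

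The last two rows are two readings of the interruption limit and bound the answer from above. Both risk statements in fact begin earlier, at visit 1 or screening. Adding the full 28 screening days lowers the Synopsis row to 10/158 = 6.3%.

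**Does AE capture close the gap?** If a participant's pregnancy were treated as an AE, capture would run to (10 + 91)/130 = 77.7% of the window, and the last 120 − 91 = 29 days would remain. But Section 8.2.1 does not define pregnancy as an AE, and its definition concerns the participant, so a partner's pregnancy is not clearly included. A congenital anomaly is a serious event under Section 8.2.2, but a birth from a conception in this window would normally come after the 3-month limit.

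**Does the trigger mean conception or detection?** The only pregnancy test in the Schedule of Events is at screening, within 72 hours before SBRT (Section 6.2.5). No later test is scheduled, so a conception during treatment may come to light only afterwards. The documents do not say which date decides whether it falls under 8.6.3.

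**The case against.** The strongest counter-argument is that a contraception period and a reporting period serve different purposes, so a difference between them is not by itself a contradiction. That stands as a general point. Here, though, the only ground given for birth control up to day 120 is possible harm to a fetus or to sperm, which is also the kind of harm the follow-up in 8.6.3 would detect. The protocol gives no reason for the shorter period.

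Second, Section 5.3.2 and the partner clause turn on becoming pregnant during treatment, and the 24-hour clock in 8.6.3 runs from learning of the pregnancy. On a natural reading, a conception during treatment that is found later is covered. This stands for those two clauses. The participant clause in 8.6.3 remains ambiguous.

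Third, other routes may exist. Section 8.2.1 words the AE period more broadly, 8.6.3 requires any SAE during pregnancy to be reported, and 8.6.1 defers to institutional IRB guidance that is not in the documents. None of these clearly closes the gap, but they rule out saying that such pregnancies would in practice go unreported.

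A reader might infer that most exposed pregnancies would be missed. The documents do not support that:
- The percentages are shares of time. They become shares of pregnancies only with a constant conception rate, and no rate is given.
- A pregnancy conceived after the last fraction was not irradiated in utero. What remains is the risk to gametes.
- Not expressly required is weaker than unreported.

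Nor does the projected 11 men show that partner pregnancies would be the larger group, because nothing is said about partners' ages or fertility.

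**Conclusion.** The mismatch is real and visible in the text. The explicit reporting and follow-up duty covers about 7% to 10% of the period from first dose to day 120 after the last dose as planned, and no more than about 32% to 35% under the longest tolerated interruptions. In every scenario at least about 65% of that time lies outside it.

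The result rests on reading the trigger as the span from first to last fraction, and on counting the risk period from first dose. It says nothing about how many pregnancies would be affected. That number is assumed to be very small: 15 participants, about 4 projected to be women (Table 1), a pre-treatment test and required contraception. The documents give neither an age distribution nor a pregnancy rate. This is a low-frequency gap in safety reporting and touches no endpoint, estimate or analysis. It is still worth correcting, because the stated rule is narrower than the protocol's own risk period.

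**What to change.** Reconcile the reporting and outcome follow-up triggers in Sections 8.6.3 and 5.3.2 with the risk period stated in Section 5.3.1 and exclusion criterion 7, for participants and for partners. State whether the date of conception or the date of detection decides that a pregnancy is in scope, and from what point the period starts. If a narrower reporting period is intended, give the reason. The change concerns the scope of reporting only; the contraception requirements and the removal-from-study provision in 5.3.2 need not change for this purpose.

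The existing CRF, IRB and 24-hour route can be used. Follow-up visits at 6 weeks and then every 3 months (Section 6.5) already give staff an occasion to learn of a pregnancy, so no visit or test is added. The cost is an amendment to the wording of two sections and, rarely, an extra report with its monthly contact to the end of the pregnancy (5.3.2) and, for a partner, her consent (8.6.3).
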